6.2 FIDELITY

6.2.1 INTERVENTIONIST TRAINING AND TRACKING

Explicit coach selection criteria and on-going monitoring and supervision of treatment delivery and fidelity will ensure that the interventions are of the highest quality, follow the protocols precisely, and prevent coach drift and contamination. For IBMT and HE, the coach must have a minimum of a master's degree in psychology, social work, or a related field and experience running group therapy. The coach will need to meet additional criteria: have completed the trainer course, had a daily practice of mindfulness, and attended a silent meditation retreat. To monitor coach's adherence and competence, all sessions will be recorded and a random sample of 10% will be rated by the investigators using the modified Adherence Scale to ensure the interventionist has adequate competence and adherence to the protocols, and to prevent drift.

6.3 MEASURES TO MINIMIZE BIAS: RANDOMIZATION AND BLINDING

To minimize potential biases, participants are randomized based on automatic covariate conducted by Co-I using an adaptive algorithm. Participants are blinded to the intervention. Specifically, they were told that they will be engaged in body-mind intervention, without knowing whether or not the intervention they received is the experimental manipulation or control intervention. See methods of analysis in Section 9, Statistical Considerations for details on randomization. Additionally, research staff who assesses participants are also blinded of the participants' intervention condition. Randomization code is maintained by different research staff. A planned breaking of randomization code and blinding would occur for any

participants who reported serious adverse events. The PI and Co-I will identify which group the participant is in, without the need for research staff to be involved in knowing the participant's intervention group.

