5.2 EXCLUSION CRITERIA

An individual who meets any of the following criteria will be excluded from participation in this study:

1. Medical disorders or medications that affect the central and autonomic nervous system; or a positive pregnancy test result (females)
2. Unable to provide consent or understand study procedures due to mental illness or cognitive limitations
3. Previous meditation experiences
4. Evidence of illicit drug use
5. Metal or metallic materials in the body such as pacemaker

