6 STUDY INTERVENTION(S) OR EXPERIMENTAL MANIPULATION(S)

6.1 STUDY INTERVENTION(S) OR EXPERIMENTAL MANIPULATION(S) ADMINISTRATION

6.1.1 STUDY INTERVENTION OR EXPERIMENTAL MANIPULATION DESCRIPTION

Experimental Manipulation – IBMT (Arm 1): IBMT emphasizes the cooperation between body and mind in facilitating and achieving a meditative state ecologically.^{1-7,18-22} Each IBMT session is facilitated by an experienced and certified coach who has demonstrated the ability to attain the appropriate state of body and mind, and to lead the group to achieve a similar state. The coach creates a harmonious and relaxed atmosphere, observes facial and body cues to identify those who are struggling with the method, and gives proper feedback for effective practice. IBMT coach helps subjects attain desired state by first providing a brief period to induce a cognitive or emotional state that will facilitate

the training. Then, coach helps subjects find an appropriate and balanced body posture and follow instructions to achieve deeper levels of relaxed body (physiology of relaxation) and experience a restful feeling and mental quiet (psychology of relaxation) mindfully.

When the mind wanders, the coach helps subjects accept and be open to experiences without judgment, and further guides subjects to use a favorite mental image as a tool to return to the present moment gently. At last, the coach facilitates a brief group discussion to ensure subjects having positive experiences consistent with the intent of IBMT. The method stresses no effort to control thoughts, but instead emphasizes a state of restful alertness that allows a high degree of awareness of the body, mind, and environment.^{1-7,18-22}

Control Intervention – Health Education (Arm 2): For HE, each session includes pre-, post- and practice sessions, similar to IBMT procedure and is facilitated by a trained coach. However, HE involves teaching participants different health promotion skills, behavior, attitude and strategies, which are guided by the certified coach. Participants have an active group experience that is not mindfulness-related. Therefore, HE induces a comparable but different experience and could serve as an ideal active control. Moreover, other groups have been using HE as active control in RCTs involving mindfulness intervention as an active control condition.^{2,7,64,65}

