8 STUDY ASSESSMENTS AND PROCEDURES

8.1 ENDPOINT AND OTHER NON-SAFETY ASSESSMENTS

The study involves assessing participants at baseline, post-intervention, and 3-month follow-up. The participant will be screened for eligibility after consenting. They will fill out demographic questionnaires and MRI screening form to determine their eligibility. Next, they will undergo behavioral, cognitive, and brain assessments by trained research staff and/or MRI technician. All non-brain assessments will be conducted at PI's lab for all participants to decrease variability. All brain assessments will be conducted at Barrow Neurological Institute for all participants to decrease variability.

Below is a list and description of the assessments:

- **Performance-based assessments**
Cognitive assessments – N-Back working memory is a memory performance test
- **Administration of questionnaires, interviews**
Behavioral assessments – Emotional Regulation Questionnaire assesses emotion regulation, Five Facet Mindfulness Questionnaire assesses mindfulness, Subjective Cognitive Decline questionnaire assesses subjective report of cognitive decline
- **Imaging assessments**
MRI Scan – provides images of brain structure and function

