9.4.2 ANALYSIS OF THE PRIMARY ENDPOINT(S)

The primary endpoints are behavioral and cognitive assessments and are all repeated measures assessed at baseline, post-intervention, and 3-month follow-up. For cognitive assessment of N-Back working memory, percentage of correct trials will be calculated for each trial for all endpoints. For behavioral assessment of emotion regulation, mindfulness, and SCD, these self-report questionnaires will be calculated based on established scoring guides by summing all items within a given questionnaire for all endpoints. Next, the effects of intervention (IBMT vs. HE) on each of these primary endpoints will be examined using repeated-measures ANOVA with time x group interaction effect. Variance and covariance across repeated measures will be calculated as part of the ANOVA. Age and sex will be included as covariates to control for potential confounding effects of age and sex on behavioral and cognitive assessments. Results will be presented as F values for the interaction effect, along with p values to indicate statistical significance. Normality and homogeneity of variance assumptions will be checked using SPSS built-in tools for ANOVA. Because there are 4 primary endpoints, multiple comparison corrections will be conducted using FDR correction. Missing data will be handled with case-wise deletion.

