10 SUPPORTING DOCUMENTATION AND OPERATIONAL CONSIDERATIONS

10.1 REGULATORY, ETHICAL, AND STUDY OVERSIGHT CONSIDERATIONS

10.1.1 INFORMED CONSENT PROCESS

10.1.1.1 CONSENT/ASSENT AND OTHER INFORMATIONAL DOCUMENTS PROVIDED TO PARTICIPANTS

Consent forms describing in detail the study intervention, study procedures, and risks will be given to the participant and written documentation of informed consent will be completed prior to starting the study intervention. The following consent materials are submitted with this protocol: Consent Form, see Section 12 Attachment.

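### Participant masking is doubtful and untested, and three of the four primary endpoints are self-rated, so a self-report difference could partly reflect expectancy

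*Combined protocol and SAP*

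**What the plan says.** Section 6.3 states that participants are blinded and then explains how: "they were told that they will be engaged in body-mind intervention, without knowing whether or not the intervention they received is the experimental manipulation" or the control. It adds that the staff who assess participants are blinded too.

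Section 6.1.1 describes the control content: "HE involves teaching participants different health promotion skills, behavior, attitude and strategies". The same section says this group experience is unrelated to mindfulness, that HE sessions are structured much like IBMT sessions, and that a trained coach leads them. Section 6.1.2 gives both arms 10 group sessions.

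On the outcomes, Section 9.4.2 says "Because there are 4 primary endpoints, multiple comparison corrections will be conducted using FDR correction". Three are questionnaires: "For behavioral assessment of emotion regulation, mindfulness, and SCD, these self-report questionnaires will be calculated based on established scoring guides". The fourth is a performance test: "For cognitive assessment of N-Back working memory, percentage of correct trials will be calculated".

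Section 10.1.1.1 says "Consent forms describing in detail the study intervention, study procedures, and risks will be given to the participant". Section 5.2 excludes people with "Previous meditation experiences".

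**The concern.** The phrase given to everyone, body-mind intervention, is also the name of the tested programme in the title and synopsis (Section 1.1). An IBMT participant receives what the phrase suggests. An HE participant receives health teaching, after a screening question about meditation and a consent form that describes the intervention in detail. She may work out that she is a control.

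This matters because of who scores the outcomes. Section 8.1 says the "Subjective Cognitive Decline questionnaire assesses subjective report of cognitive decline", and emotion regulation and mindfulness are also self-rated. For these three the participant is the assessor, so staff blinding does not help. The mindfulness questionnaire is especially exposed, because IBMT teaches what it asks about. A time x group difference could then contain some expectation in IBMT or disappointment in HE. Section 9.2 says the study is meant to gauge an effect size before a larger trial, so an inflated self-report estimate would carry forward.

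**Working it through.** **Count of exposed endpoints.** Section 9.4.2 states 4 primary endpoints. Counting those it names gives N-Back (performance) plus emotion regulation, mindfulness and SCD (self-report) = 4, so 3 of 4 are self-rated. The objectives table in Section 3 omits N-Back, which makes it 3 of 3. The primary hypothesis in Section 9.1 names working memory, emotion regulation and SCD, which makes it 2 of 3. Self-report is the majority in each.

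**Is masking tested?** The schedule (1.3), the assessments (8.1) and the analysis sections (9.4.1 to 9.4.9) contain no credibility or expectancy rating, no allocation guess and no related sensitivity analysis. The per-session self-report in Section 6.4 covers engagement and quality of practice, which is a different matter.

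**Is the experience symmetrical?** Section 6.1.1 has the IBMT coach close with a group discussion meant to secure positive experiences in line with the method's intent. It describes no counterpart for HE.

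**What would a bias do?** The documents give no value for expectancy bias, so its size b is assumed over a range.

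Inputs:
- N = 36, from 40 recruited with 10% dropout (Section 5.5), taken as 18 per arm
- three visits, time x group test, FDR over four endpoints (Section 9.4.2), alpha 0.05 (Section 9.2)
- correlation of repeated behavioural measures rho = 0.3 to 0.6 (Section 9.2)
- assumed: no true effect; a shift of b SD between arms at both post-baseline visits on each self-report; self-reports correlated 0.3 with each other; N-Back unaffected; equal correlations between visits; no age and sex covariates

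The between-arm difference over the three visits is (0, b, b). Its deviations from the mean are (-2b/3, b/3, b/3), with sum of squares 2b²/3. The noncentrality is therefore

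lambda = (N/4) x (2b²/3) / (1 - rho) = 6b²/(1 - rho) for N = 36,

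on 2 and 68 degrees of freedom. For b = 0.5, lambda is 6 x 0.25/0.7 = 2.14 at rho = 0.3 and 6 x 0.25/0.4 = 3.75 at rho = 0.6.

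The single-endpoint columns come from the noncentral F distribution. The last two columns come from simulating the ANOVA on all four endpoints and applying the Benjamini-Hochberg step.

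| b (SD) | One endpoint, unadjusted, rho 0.3 | One endpoint, unadjusted, rho 0.6 | Any self-report after FDR, rho 0.3 | Any self-report after FDR, rho 0.6 |
|---|---|---|---|---|
| 0 | 5% | 5% | about 4% | about 4% |
| 0.2 | 7.6% | 9.6% | about 7% | about 9% |
| 0.3 | 11.0% | 15.9% | about 10% | about 17% |
| 0.4 | 16.1% | 25.4% | about 17% | about 29% |
| 0.5 | 23.0% | 37.7% | about 25% | about 44% |

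With N = 40 the unadjusted single-endpoint figures are slightly higher: 7.9% to 10.1% at b = 0.2 and 25.3% to 41.6% at b = 0.5. FDR controls chance findings among true nulls. It does nothing about a shift produced by bias.

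**The case against.** The best defence is that 6.3 makes a limited claim. The sentence after the word blinded defines it as not knowing which arm is experimental, and a person can know she attends health education without knowing it is the comparator. That reading is fair. A reader might infer that blinding cannot hold and that HE participants know from the first session that they are controls. The documents do not support that: the consent form is not in the reviewed text, and it may present two programmes neutrally. The meditation exclusion is at most a cue.

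The control is also a real protection. HE is an active comparator with 10 group sessions, similar session structure, and the same coach qualifications and fidelity monitoring (Section 6.2.1). This balances attention and contact and should narrow any difference in expectation. It does not make a body-mind label an apt description of health teaching, and no measure would show whether expectations were in fact balanced.

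It can also be said that the calculation only shows that bias, if present, raises false positives. That stands, and the table is an illustration over assumed values. Finally, this is a pilot, and incomplete masking is common in behavioural trials. That limits the severity, but it does not justify leaving an inexpensive check out.

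**Conclusion.** The point holds as a risk that is neither acknowledged nor measured. Masking to arm status rests on a description that suits one arm better than the other, most primary endpoints are self-rated, and no planned item would reveal a problem.

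A reader might go further and conclude that self-report differences in this trial do carry expectancy bias. The documents give no evidence of its presence, direction or size, so that does not follow.

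Under the assumptions listed, a pure expectancy difference of 0.2 to 0.5 SD would raise the chance of at least one significant self-report endpoint from about 4% to between 7% and 25% (rho 0.3) or between 9% and 44% (rho 0.6). The range depends mainly on b, which is unknown. The change is worth making because, without such items, the bias could not be assessed afterwards.

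**What to change.** 1. In Section 6.3, the recruitment material and the consent wording, use one description that is true of both arms, for example 'one of two group wellness programmes being compared'.
2. Add a short credibility and expectancy rating after session 1 and report it by arm. If an allocation-guess item is wanted, place it after the Visit 13 outcome measures. At Visit 12 it would come before the three-month self-reports and could prime them. A late guess will partly reflect perceived benefit, so the early rating is the more informative of the two.
3. Restate Section 6.3 as 'outcome assessors blinded; participants not told which programme is experimental'.
4. State in Section 9.4.2 that a self-report difference without an N-Back difference is reported as a change in self-report only. This needs N-Back to be named in the schedule (1.3) and the objectives table (3), where it is now absent.

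The cost is an IRB amendment for wording, about two minutes per participant, and a more limited claim if only the self-reports move.

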6.4 STUDY INTERVENTION/EXPERIMENTAL MANIPULATION ADHERENCE

Participants' adherence with study procedures will be tracked by taking their attendance at intervention visits. Moreover, in each session, we use participant self-report and coach observation to calculate study intervention adherence by the participant based on their engagement and quality of practice.

6.5 CONCOMITANT THERAPY

N/A

6.5.1 RESCUE THERAPY

N/A

7 STUDY INTERVENTION/EXPERIMENTAL MANIPULATION DISCONTINUATION AND PARTICIPANT DISCONTINUATION/WITHDRAWAL

7.1 DISCONTINUATION OF STUDY INTERVENTION/EXPERIMENTAL MANIPULATION

If a clinically significant finding is identified (including, but not limited to changes from baseline) after enrollment, the investigator or qualified designee will determine if any change in participant management is needed. Any new clinically relevant finding will be reported as an adverse event (AE).

The data to be collected at the time of study intervention discontinuation will include the following:

- The reason(s) for discontinuing the participant from the intervention, and methods for determining the need to discontinue
- If the participant is due to complete assessments within 1 weeks of being discontinued from the study intervention, those assessments will be administered at the time of discontinuation; if the next scheduled assessments are more than 1 week from the discontinuation date, the next scheduled assessment will not be administered. Thereafter, the participant will be not included in all future scheduled assessments, as they did not participate in the intervention.

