1.3 SCHEDULE OF ACTIVITIES

| | Screening | Visit 1 Day 1 | Visit 2 to Visit 11 Day 3 ±1 to Day 12 ±1 | Visit 12 Day 13 ±2 | Visit 13 Day 90 ±2 |
|---|-----------|------------------|--|-----------------------|-----------------------|
| Review Eligibility | X | | | | |
| Informed Consent | | X | | | |
| Demographics | | X | | | |
| Outcome Evaluation | | | | | |
| Behavioral Assessment (Emotion Regulation Questionnaire; Five Facet Mindfulness Questionnaire; Subject Cognitive Decline Questionnaire) | | X | | X | X |
| Brain Assessment (MRI scan) | | X | | X | X |
| Randomization | | X | | | |
| Control & Experimental Interventions | | X | X | | |
| Adverse Events Reporting | | X | X | X | X |

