7.2 PARTICIPANT DISCONTINUATION/WITHDRAWAL FROM THE STUDY

Participants are free to withdraw from participation in the study at any time upon request.

An investigator may discontinue a participant from the study for the following reasons:

- Significant study intervention non-compliance, unless varying compliance is an aspect of the study objectives
- Lost-to-follow up; unable to contact subject (see **Section 7.3, Lost to Follow-Up**)
- Any event or medical condition or situation occurs such that continued collection of follow-up study data would not be in the best interest of the participant or might require an additional treatment that would confound the interpretation of the study

- The participant meets an exclusion criterion (either newly developed or not previously recognized) that precludes further study participation

The reason for participant discontinuation or withdrawal from the study will be recorded. Subjects who sign the informed consent form and are randomized but do not receive the study intervention may be replaced. Subjects who sign the informed consent form, and are randomized and receive the study intervention, and subsequently withdraw, or are discontinued from the study, will not be replaced.

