9 STATISTICAL CONSIDERATIONS

9.1 STATISTICAL HYPOTHESES

- Primary Endpoint(s):

We hypothesize that, compared to participants who receive a control intervention, participants who receive IBMT for improving behavior and cognition will have improved working memory, emotion regulation, and reduced subjective report of cognitive decline after completing the intervention at post-assessment, and will continue to show improvement 3 months after the intervention. Alternatively, our null hypothesis is that there will be no difference in the effects of IBMT for improving behavior and cognition and those of control intervention at post-assessment or after 3 months of intervention.

- Secondary Endpoint(s):

We hypothesize that, compared to participants who receive a RT control intervention, participants who receive IBMT for improving brain function and structure will have improved white matter, grey matter, and functional connectivity in AD-signature regions after completing the intervention at post-assessment, and will continue to show improvement 3 months after the intervention. Alternatively, our null hypothesis is that there will be no difference in the effects of IBMT for improving brain function and structure and those of RT at post-assessment or after 3 months of intervention.

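### Section 7.1 ends Day 90 collection, and for early stoppers Day 13 collection, after discontinuation from the sessions, so an all-randomised analysis would need untestable assumptions, and none is planned

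*Combined protocol and SAP*

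**What the plan says.** Section 7.1 governs collection once a participant is discontinued from the intervention. If the next assessment is due within a week, "those assessments will be administered at the time of discontinuation". Otherwise, "if the next scheduled assessments are more than 1 week from the discontinuation date, the next scheduled assessment will not be administered". It ends: "Thereafter, the participant will be not included in all future scheduled assessments, as they did not participate in the intervention".

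The Section 1.3 schedule puts the sessions at "Visit 2 to Visit 11 Day 3 ±1 to Day 12 ±1", the post-intervention assessment at "Visit 12 Day 13 ±2", and the follow-up at Visit 13, Day 90 ±2. Section 9.1 compares the arms at post-assessment and predicts that IBMT participants "will continue to show improvement 3 months after the intervention".

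Section 9.3 restricts the analysis population to participants with all ten sessions and full primary-endpoint data. Section 9.4.2 specifies repeated-measures ANOVA and removes cases with missing values.

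On replacement, Section 7.2 says: "Subjects who sign the informed consent form and are randomized but do not receive the study intervention may be replaced". Those who receive the intervention and "subsequently withdraw, or are discontinued from the study, will not be replaced".

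**The concern.** Stopping the sessions is not the same as withdrawing consent. Section 7.1 treats the two alike for outcome collection, so data are lost by rule from people who may still be reachable and willing. This sits oddly beside the retention measures in Section 5.5 and the contact attempts in Section 7.3. The reason given, that these people did not take part, also conflicts with Section 7.2, which recognises a group who received the intervention and then left.

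IBMT and health education differ in content, so stopping could differ by arm and be related to outcome. A comparison of those who remain would then no longer be the randomised comparison that Section 9.1 describes. An analysis population can be redefined later, but an outcome that was never measured can only be modelled. Section 9.2 gives learning the effect size ahead of a larger study as a purpose of this pilot, so a distorted estimate would carry forward.

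**Working it through.** **1. The plan's own figure.** Section 5.5: 40 recruited, 10% dropout. 40 × (1 − 0.10) = 36 completers, as stated. The 5–10% range quoted there is 2 to 4 people.

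**2. What the one-week rule does.** Inputs: post-assessment Day 13, follow-up Day 90 (Section 1.3), threshold 7 days (Section 7.1). The cut-off is 13 − 7 = Day 6.

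| Stop day | Days to Day 13 | Post-assessment | Days to Day 90 | Follow-up |
|---|---|---|---|---|
| 1–5 | 12 to 8 | none | 89 to 85 | none |
| 6–12 | 7 to 1 | on the stopping day, 1–7 days early | 84 to 78 | none |

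With Visit 12 at Day 11 or Day 15, the cut-off moves to 11 − 7 = Day 4 or 15 − 7 = Day 8. The Day 90 result is the same throughout.

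**3. The stated reason.** At one session a day from Day 3, a person who stops after the Day 5 session has attended 5 − 3 + 1 = 3 sessions. That person did participate, yet has no outcome after baseline.

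**4. Possible bias.** If an arm's mean is taken from completers only, bias = (share missing) × (gap between completers and stoppers). For the arm difference, bias = p₁ × gap₁ − p₀ × gap₀. Assumptions: 20 per arm, all 4 planned dropouts are stops, and a gap of 0.3 to 0.8 SD.
- 2 stops in each arm, equal gaps: 0.10 × gap − 0.10 × gap = 0.
- All 4 in one arm: 4/20 × 0.3 = 0.06 SD; 4/20 × 0.8 = 0.16 SD.
- For scale, the standard error with 16 and 20 completers is √(1/16 + 1/20) = 0.34 SD, so this bias is about 0.2 to 0.5 of a standard error.

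**5. Without assumptions about the missing values.** Width of worst-case bounds on the Day 90 difference = (m₁/n₁ + m₀/n₀) × scale range.
- 1 missing of 20 per arm: 0.05 + 0.05 = 10% of the range.
- 2 missing of 20 per arm: 0.10 + 0.10 = 20% of the range, or 20 points on N-Back percent correct.

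**6. Can a model recover the answer?** Illustrative simulation with assumed inputs: 20 per arm, correlation 0.5, effect 0.6 SD, 4000 runs.

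| Why IBMT participants stop | Missing in IBMT arm | Full data | Raw completers | Baseline-adjusted | Reference-based imputation |
|---|---|---|---|---|---|
| Depends on baseline, benefit retained | 19% | 0.60 | 0.71 | 0.60 | 0.48 |
| Unrelated to baseline, no benefit in stoppers | 15% | 0.51 | 0.60 | 0.60 | 0.51 |

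Each method is right in one case and wrong in the other. With no outcomes from stoppers, the data cannot show which case applies.

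**The case against.** Several points on the other side stand.

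- The one-week rule preserves a post-assessment for nominal stops on Days 6–12, which is 7 of the 10 session days. A reader might infer that Section 7.1 ends all outcome assessment. It does not, although the retained value is taken early.
- A reader might also infer that no analysis could recover the effect in all randomised participants. That is too strong: baseline values and some early post-assessments permit bounding, model-based or reference-based analyses.
- Early values from part-attenders do not contaminate the planned analysis, because Section 9.3 already excludes those people. For the same reason, changing Section 7.1 alone would alter no planned result.
- Replacement is optional and limited to people who received no intervention. It erases nobody's data, and the documents do not support reading it as substitution for people who stop partway.
- The rule applies to participants who are discontinued. Someone who only misses sessions can still be assessed, and Section 7.3 provides for rescheduling.
- Section 5.5 attributes dropout to illness or relocation over the whole study. Treating all of it as stopping the sessions is an assumption, and some of these people could not attend later visits anyway.
- Any bias of the size shown is below one standard error in a study described as a pilot.

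These points narrow the concern but do not remove it. Day 90 is still lost for every discontinued participant, by rule, and Day 13 for the early ones. A bias smaller than the sampling error is no reason to forgo data that are cheap to collect.

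**Conclusion.** The concern holds in a limited form. Section 7.1 removes Day 90 outcomes for everyone discontinued from the sessions. It also removes Day 13 outcomes for those who stop more than a week before Visit 12, for a reason that is untrue of part-attenders. What is lost is an estimate for all randomised participants that does not depend on untestable assumptions; estimation under stated assumptions remains possible, but the plan contains no such analysis.

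The size is uncertain because the documents give no rate of stopping. The range of 0 to 0.16 SD takes the planned dropout as all stops, 20 per arm, and either an even split with equal gaps (zero) or all 4 in one arm with an assumed 0.3 to 0.8 SD gap (0.06 to 0.16 SD). Replacement under Section 7.2 is a secondary matter of reporting. Because Section 4.1 randomises before baseline, a replaced non-starter may have no outcome data at all and should at least remain visible in the participant flow.

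**What to change.** Three linked changes are needed:

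1. **Section 7.1.** Replace the early assessment and the exclusion from later ones with: participants who stop the sessions but do not withdraw consent are invited to Visit 12 (Day 13) and Visit 13 (Day 90) at the originally scheduled times, for questionnaires, N-Back and, if willing, MRI.
2. **Sections 9.3 and 9.4.** Add an analysis of all randomised participants by assigned arm that uses these data, for example a mixed model for repeated measures, with its missing-data assumption stated. Without this step the new data would go unused.
3. **Reporting.** Account for every randomised participant in the flow, including any non-starter replaced under Section 7.2.

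This changes data collection and analysis only, not who stops the sessions or why. The cost is a short amendment and up to two visits for each of about 4 participants (4 × 2 = 8 visits at most), all of types already in the schedule. Section 5.5 already provides prorated compensation. Some stoppers will decline, particularly the MRI, so missing data will be reduced but not eliminated.
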